#### 7.1.1. Liver Chemistry Stopping Criteria

Liver chemistry stopping and increased monitoring criteria have been designed to assure participant safety and evaluate liver event etiology.

[figure not shown]
Discontinuation of study intervention (daprodustat) for abnormal liver tests is required when:

- a participant meets one of the conditions outlined in the Liver Stopping and Monitoring Event Algorithm (Figure 6), or
- in the presence of abnormal liver chemistry not meeting protocol-specified stopping rules, if the investigator believes that it is in the best interest of the participant.

TMF-15144431

214066 Protocol Amendment 02

Figure 6 Liver Stopping and Monitoring Event Algorithm

[figure not shown]
- Must refer to Liver Safety Required Actions and Follow up Assessments section in the Appendix
- > Report within 24 hours
- ▶ If possible Hy's Law case: ALT≥3xULN and total bilirubin ≥2xULN (>35% direct) or INR>1.5\* report as an SAE
  \*INR value not applicable to participants on anticoagulants

Abbreviations: ALT = alanine aminotransferase; INR = international normalized ratio; SAE = serious adverse event; ULN = upper limit of normal

If the ALT is  $\ge 3 \times \text{ULN}$  but  $< 8 \times \text{ULN}$  and according to Figure 6 study intervention (daprodustat) can be continued with increased liver chemistry monitoring, the increased liver chemistry monitoring should be performed as shown in Figure 7.

214066 Protocol Amendment 02

Figure 7 Liver Chemistry Increased Monitoring Algorithm with Continued Study Intervention for Participants with ALT ≥3×ULN but <8×ULN

Abbreviations: ALT = alanine aminotransferase; INR = international normalized ratio; SAE = serious adverse event; ULN = upper limit of normal

Refer to Appendix 5 for required Liver Safety Actions and Follow-up Assessments.

#### 7.1.2. QTc Stopping Criteria

There is no QTc stopping criterion, as per the adult Phase 3 studies, in view of the reassuring Thorough QT study and no concerns identified to date.

## 7.1.3. Temporary Discontinuation

As described in Table 11 in Section 4.6, if the Hgb is >12.5 g/dL, daprodustat should be temporarily withheld and checked in 4 weeks at the next study visit (or from Study Week 28 an extra Hgb check Visit should be performed 4 weeks later if the next scheduled visit is not within that timeframe). Restart is permitted at the next lower dose when the Hgb is  $\le 12.0$  g/dL.

#### CONFIDENTIAL

214066 Protocol Amendment 02

## 7.1.4. Rechallenge

## 7.1.4.1. Study Intervention Restart or Rechallenge after liver stopping criteria met

Study intervention restart or rechallenge after liver chemistry stopping criteria are met by any participant in this study is not allowed.

## 7.2. Participant Discontinuation/Withdrawal from the Study

The legal guardian and the pediatric participant have the right to withdraw permission (consent or assent, respectively) at any time during the study. If the study staff identify any reluctance in the legal guardian or pediatric participant (e.g., signs of verbal or physical dissent) about continued participation in the study, the pediatric participant's continuation in the study should be re-evaluated. The same principles that govern permission/assent/consent also govern its withdrawal.

A participant will be withdrawn from the study for the following reason:

- Withdrawal of consent or assent if applicable (a pediatric participant's dissent should be respected).
- Undergoes a kidney transplant.

At the time of discontinuation from the study, if possible, an early discontinuation visit should be conducted. See the SoA (Section 1.3) for data to be collected at the time of study discontinuation and follow-up and for any further evaluations that need to be completed. The participant will be permanently discontinued both from the study intervention (if applicable) and from the study at that time.

If the participant withdraws consent for disclosure of future information, the sponsor may retain and continue to use any data collected before such a withdrawal of consent.

If a participant withdraws from the study, he/she may request destruction of any samples taken and not tested, and the investigator must document this in the site study records.

## 7.3. Lost to Follow-Up

A participant will be considered lost to follow-up if he or she repeatedly fails to return for scheduled visits and is unable to be contacted by the study site.

The following actions must be taken if a participant fails to return to the clinic for a required study visit:

 The site must attempt to contact the participant and reschedule the missed visit as soon as possible and counsel the participant on the importance of maintaining the assigned visit schedule and ascertain whether the participant wishes to and/or should continue in the study.

TMF-15144431 CONFIDENTIAL

214066 Protocol Amendment 02

- Before a participant is deemed lost to follow-up, the investigator or designee must make every effort to regain contact with the participant and/or caregiver (where possible, 3 telephone calls and, if necessary, a certified letter to the participant's last known mailing address or local equivalent methods). These contact attempts should be documented in the participant's medical record.
- Should the participant continue to be unreachable, he/she will be considered to have withdrawn from the study.
- Site personnel, or an independent third party, will attempt to collect the vital status of the participant within legal and ethical boundaries for all participants enrolled, including those who did not get study intervention. Public sources may be searched for vital status information. If vital status is determined as deceased, this will be documented and the participant will not be considered lost to follow-up. Sponsor personnel will not be involved in any attempts to collect vital status information.

Discontinuation of specific sites or of the study as a whole are handled as part of Section 10.1.9.

214066 Protocol Amendment 02

#### 8. STUDY ASSESSMENTS AND PROCEDURES

Study procedures and their timing are summarized in the SoA (Section 1.3).

Protocol waivers or exemptions are not allowed.

Where applicable country and local regulations and infrastructure for home healthcare allow, home healthcare may take place at home or alternative approved locations other than the clinical trial site to perform study assessments (at the discretion of the investigator). The site may work with GSK to use a centrally appointed home nursing vendor for conduct of study assessments.

Immediate safety concerns should be discussed with the sponsor immediately upon occurrence or awareness to determine if the participant should continue or discontinue study intervention.

Adherence to the study design requirements, including those specified in the SoA, is essential and required for study conduct.

All screening evaluations must be completed and reviewed to confirm that potential participants meet all eligibility criteria. The investigator will maintain a screening log to record details of all participants screened and to confirm eligibility or record reasons for screening failure, as applicable.

Procedures conducted as part of the participant's routine clinical management (e.g., blood count) and obtained before signing of ICF may be utilized for screening or baseline purposes provided the procedure met the protocol-specified criteria and was performed within the timeframe defined in the SoA (Section 1.3).

The maximum amount of blood collected from each participant over the duration of the study does not exceed recommendations for blood sampling in a pediatric population by age or weight (see Table 12).

Race and ethnicity will be collected for all participants in order to satisfy regulatory requirements for some jurisdictions and to allow appraisal of the extent to which disadvantaged and minority groups are represented in the trial population.

## 8.1. Efficacy Assessments

The dose response of participants to daprodustat will be assessed by measurement of Hgb. Hgb also serves to determine where a dose change is needed, see Section 4.6.

Planned timepoints for all Hgb assessments are provided in the SoA. Hgb should be checked and the dose adjusted if required, as defined in the protocol in Section 4.6 and Section 4.5 respectively.

#### CONFIDENTIAL

214066 Protocol Amendment 02

## 8.2. Safety Assessments

Planned time points for all safety assessments are listed in the SoA (Section 1.3). Additional time points for safety tests (such as vital signs, physical examinations and laboratory safety tests) may be added during the course of the study based on newly available data to ensure appropriate safety monitoring.

## 8.2.1. Physical Examinations

Children and adolescents with CKD, particularly those with ESKD, are frequently growth impaired, so at a given age, they can often be expected to have the weight of a smaller/younger child/adolescent.

Height (or supine length in the very young) and weight will be measured at each study visit as appropriate for the participant's age and plotted on age and gender appropriate charts as per SoC at that site, for example using height z scores for chronological age and body mass index (BMI) z scores for height age (the age corresponding to the 50th percentile of the participant's measured height) as a means of monitoring percentile-parallel growth and weight gain. Any unexpected persistent change in trajectory, should be recorded as an AE.

The investigator should contact the medical monitor if any participant's weight falls below that specified as the minimum weight for their age group (see Table 12).

A complete physical examination will include, at a minimum, assessments of the ears, nose and throat, skin, cardiovascular, respiratory, GI and neurological systems.

### 8.2.2. Vital Signs

Vital signs will include systolic and diastolic BP and HR.

BP and HR will be assessed using an appropriate size cuff. BP and HR should be preceded by at least 5 minutes of rest for the participant in a quiet setting without distractions (e.g., television, cell phones). Three consecutive BP measurements will be obtained, of which the median will be recorded.

## 8.2.3. Electrocardiogram

A 12-lead ECG for screening exclusion criterion (see Section 5.2) will be obtained in the supine position. HR, PR interval, QRS duration and QT (uncorrected) interval will be measured. QTcF will be calculated (machine-read or manually). If prolonged QT/QTcF is noted, 2 additional ECGs measurements should be obtained. Determination of whether eligibility criteria are met will be based on the average of the triplicate assessment.

214066 Protocol Amendment 02

There is no QT stopping criteria Section 7.1.2 and no further ECG monitoring is required unless indicated as part of routine care of the participant.

## 8.2.4. Clinical Safety Laboratory Tests

See Appendix 2 for the list of clinical laboratory tests to be performed and to the SoA for the timing and frequency.

The investigator must review the local laboratory report, document this review, and record any clinically significant changes occurring during the study in the AE section of the eCRF. The laboratory reports must be available as source documents.

Abnormal laboratory findings associated with the underlying disease are not considered clinically significant, unless judged by the investigator to be more severe than expected for the participant's condition.

All laboratory tests with values considered clinically significantly abnormal during participation in the study or within 4 weeks after the last dose of study intervention should be repeated until the values return to normal or baseline or are no longer considered significantly abnormal by the investigator or study medical monitor. If such values do not return to normal/baseline within a period of time judged reasonable by the investigator, the etiology should be identified and the sponsor notified.

All protocol-required laboratory tests (as defined in Section 10.2) and the PK sampling (see Section 8.4.1), must be conducted in accordance with the SoA (Section 1.3) and the laboratory manual (for PK sampling).

If laboratory values from non-protocol-specified laboratory tests performed at the institution's local laboratory require a change in participant management or are considered clinically significant by the investigator (e.g., SAE or AE or dose modification), then the results must be recorded in the eCRF.

#### 8.2.5. Pregnancy Testing

Refer to Section 5.1 for pregnancy testing inclusion criteria.

Pregnancy testing in FOCBP should be conducted at each study visit, including the 56-week follow-up visit. Pregnancy testing may consist of a:

- serum hCG test, or
- urine hCG test if the eGFR is higher than 15mL/min/1.73m^2.

Additional serum or urine pregnancy tests may be performed, as determined necessary by the investigator, or required by local regulation, to establish the absence of pregnancy at any time during the participant's participation in the study.

214066 Protocol Amendment 02

# 8.3. Adverse Events (AEs), Serious Adverse Events (SAEs) and Other Safety Reporting

The definitions of AEs or SAEs can be found in Section 10.3.

AEs will be reported by the participant (or, when appropriate, by a caregiver, surrogate, or the participant's legally authorized representative).

The investigator and any qualified designees are responsible for detecting, documenting, and reporting events that meet the definition of an AE or SAE and remain responsible for following up AEs that are serious, considered related to the study intervention or the study, or that caused the participant to discontinue the study intervention (see Section 7.1).

The method of recording, evaluating, and assessing causality of AEs and SAEs and the procedures for completing and transmitting SAE reports are provided in Section 10.3.

## 8.3.1. Time Period and Frequency for Collecting AE and SAE Information

All AEs and SAEs will be collected from the signing of informed consent until the follow-up visit (Week 56) at the time points specified in the SoA (Section 1.3).

All SAEs will be recorded and reported to the sponsor or designee immediately and under no circumstance should this exceed 24 hours, as indicated in Appendix 3. The investigator will submit any updated SAE data to the sponsor within 24 hours of it being available.

Investigators are not obligated to actively seek information on AEs or SAEs after the conclusion of the study participation. However, if the investigator learns of any SAE, including a death, at any time after a participant has been discharged from the study, and he/she considers the event to be reasonably related to the study intervention or study participation, the investigator must promptly notify the sponsor.

## 8.3.2. Method of Detecting AEs and SAEs

#### **Clinical Presentation of Adverse Events:**

Study site staff should instruct the legal guardians and caregivers, on how to report signs and symptoms (e.g., crying and pain) in the individual pediatric participant. They will be instructed to report both specific and non-specific symptoms (including vomiting, diarrhea, sleepiness, variation in the intensity and pattern of crying, etc.). These non-specific symptoms may be the only manifestations of some adverse reaction observed in young children. Care should be taken that the clinical presentation of adverse reactions is not misinterpreted as the manifestation of a pre-existing or unrelated condition.

Care will be taken not to introduce bias when detecting an AE and/or SAE. Open-ended and non-leading verbal questioning of the participant is the preferred method to inquire

#### CONFIDENTIAL

214066 Protocol Amendment 02

about AE occurrence.

## 8.3.3. Follow-up of AEs and SAEs

After the initial AE/SAE report, the investigator is required to proactively follow each participant at subsequent visits/contacts. All SAEs, and AESIs (as defined in Section 8.3.6), will be followed until the event is resolved, stabilized, otherwise explained, or the participant is lost to follow-up (as defined in Section 7.3). Further information on follow-up procedures is given in Section 10.3.3.

## 8.3.4. Regulatory Reporting Requirements for SAEs

Prompt notification by the investigator to the sponsor of an SAE is essential so that legal obligations and ethical responsibilities towards the safety of participants and the safety of a study intervention under clinical investigation are met.

The sponsor has a legal responsibility to notify both the local regulatory authority and other regulatory agencies about the safety of a study intervention under clinical investigation. The sponsor will comply with country-specific regulatory requirements relating to safety reporting to the regulatory authority, IRB/IEC and investigators.

An investigator who receives an investigator safety report describing an SAE or other specific safety information (e.g., summary or listing of SAEs) from the sponsor will review and then file it along with the IB and will notify the IRB/IEC, if appropriate according to local requirements.

Investigator safety reports must be prepared for suspected unexpected serious adverse reaction (SUSAR) according to local regulatory requirements and sponsor policy and forwarded to investigators as necessary.

### 8.3.5. Pregnancy

Details of all pregnancies in female participants will be collected after the start of study intervention and until 30 days after the last dose of study intervention.

If a pregnancy is reported, the investigator will record pregnancy information on the appropriate form and submit it to GSK within 24 hours of learning of the female participant's pregnancy. While pregnancy itself is not considered to be an AE or SAE, any pregnancy complication or elective termination of a pregnancy for medical reasons will be reported as an AE or SAE.

Abnormal pregnancy outcomes (e.g., spontaneous abortion, fetal death, stillbirth, congenital anomalies, ectopic pregnancy) are considered SAEs and will be reported as such.

TMF-15144431 CONFIDENTIAL

214066 Protocol Amendment 02

The participant will be followed to determine the outcome of the pregnancy. The investigator will collect follow-up information on the participant and the neonate, and the information will be forwarded to the sponsor.

Any post-study pregnancy-related SAE considered reasonably related to the study intervention by the investigator will be reported to the sponsor. While the investigator is not obligated to actively seek this information in former study participants he or she may learn of an SAE through spontaneous reporting.

Any female participant who becomes pregnant while participating in the study will discontinue study intervention (Section 7.1).

## 8.3.6. Adverse Events of Special Interest

The investigator or site staff will be responsible for detecting, documenting and reporting any events that may represent the AESIs listed below (using preferred terms):

- Death, MI, stroke, HF, thromboembolic events, thrombosis of vascular access.
- Thrombosis and/or tissue ischemia secondary to excessive erythropoiesis.
- New diagnosis of hypertension or worsening of existing hypertension.
- Cancer related mortality and tumor progression and recurrence.
- Esophageal and gastric erosions.

The results of any investigation should be recorded on the AE page and the relevant AESI page of the participant's eCRF.

#### 8.3.7. Tertiary Endpoints

#### 8.3.7.1. Other Health Outcomes of Interest

The incidence of the protocol-defined health outcomes of interest listed in Section 9.3.2.4 are of particular importance in a pediatric population with anemia associated with CKD. At each visit, the investigator should indicate in the eCRF if one of these outcomes has occurred in the interval since the last study visit, ensuring that the details of any such outcomes are reported in the AE and/or concomitant medication eCRF pages as appropriate.

70

§ Worsening of existing hypertension defined as occurrence of one or more of the following:

New resistant hypertension: hypertension despite treatment with at least 3 (maximal or maximally tolerated doses of) antihypertensive medications.

Hypertensive emergency: severely elevated BP associated with acute end-organ damage.

Hypertensive urgency: severely elevated BP without the presence of acute end-organ damage.

214066 Protocol Amendment 02

### 8.3.7.2. Acceptability and Palatability Assessment

The acceptability and palatability of the 2 formulations used in this study (IR and TfOS) will be assessed by a participant questionnaire at Week 2.

#### 8.4. Pharmacokinetics

#### 8.4.1. Integrated PK Phase

Blood samples for determination of daprodustat and its major metabolites plasma concentration will be collected post dosing on Day 1, and, prior and post dosing at Week 2. If the PK samples are not convenient to perform at the Week 2 Study Visit, then these can be deferred to Week 4, as indicated in the SoA (Section 1.3). The 4 PK samples at Week 2 may also be split between Weeks 2 and 4 provided the dose of daprodustat is taken in clinic (to be sure of the exact time of dosing) and the 4 samples taken across the 2 Study Visits at Weeks 2 and 4 cover all 4 time intervals required (pre-dose, 0.5 to  $1.5 \text{ hour } \lceil h \rceil$ ,  $>1.5 \text{ to } 3 \text{ h and } \ge 4 \text{ to } 8 \text{ h}$ ).

At Day 1 and at Week 2 (or if needed at Week 4), the daily dose of daprodustat should be taken in the clinic and not at home. This information is summarized below:

#### At Day 1:

- Take the first dose whilst still in the clinic.
- Then take **3 samples:** 0.5 to 1.5 h, >1.5 to 3 h and ≥4 h time (maximum 8 h) intervals after taking the first dose of daprodustat. These limited time point samples are needed to compare with repeat dose data.

#### At Week 2 Visit (and/or at Week 4 if not fully performed at Week 2):

- Take the pre-dose sample.
- Then take the morning dose (as previously dispensed) whilst still in the clinic (the participant should not have taken the dose at home before the visit).
- Then take **3 further samples:** 0.5 to 1.5 h, >1.5 to 3 h and  $\ge 4$  h time (maximum 8 h) intervals post dose.

#### Note:

- If a participant is allocated to start on 0.125 mg QD (achieved by administration of 0.25 mg TIW), dose as normal but if a 0.25 mg tablet is due to be taken on the Week 2 (or Week 4) Visit day, the tablet should not be given at home that morning but administered in the clinic after the pre-dose blood sample is taken.
- If at Week 2, a participant has already taken their daprodustat dose prior to arrival in clinic, then reschedule the PK sampling to Week 4, reminding the participant not to take their dose at home on the day of the Week 4 visit.
- If the PK sampling is to be done at Week 4 (having been deferred from Week 2) and the participant has already taken their daprodustat at home the morning of the Week 4 Visit, omit the pre-dose sample and take those post dose samples that are

214066 Protocol Amendment 02

possible to collect for the time intervals 0.5 to 1.5 h, >1.5 to 3 h and  $\ge 4$  h time (maximum 8 h), noting the time of PK sampling in the eCRF and the participants as accurate as possible estimation of the time of home administration of daprodustat.

- If PK sampling is deferred to Week 4, but the participant has been put on dose hold at Week 2 (as the Hgb is >12.5 g/dL), then PK sampling should be delayed until the visit after daprodustat is restarted.
- PK samples can be taken before, during or after dialysis.

The date and timing (24-hour clock time) of PK sampling, daprodustat dosing and any concomitant medications taken needs to be recorded for each participant. At Week 2 (and/or Week 4), the participant needs to provide the time of last dose before the day of PK assessments (for the pre-dose trough estimation). A PK reminder card will be given to all participants undergoing PK assessments so they may record this time. This card will also serve as a reminder not to take their daprodustat dose at home on the day of the PK assessments.

Approximately 1.0 mL of blood (0.5 mL of plasma) is required for the assay. Therefore, the total blood volume for PK sampling on any occasion, and over the 2 (or 4) week sampling period in the PK Phase, will not exceed ~7 mL, ~1.09% of blood volume of a 1 year old child (assuming 80 mL/kg and 8 kg body weight). Together with the other blood draws required in the first 4 weeks, given that the minimum body weight required at study entry is 5 kg (see Table 12), the total volume of blood required will not exceed the recommended 1% blood volume draw limit per day or 3% blood volume draw limit over 4 weeks [Paediatric Population: Recommendations, 2008, Minors: Recommendations, 2017].

Processing, storage, and shipping procedures are provided in the laboratory manual.

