- e. Height (or supine length in the very young) and weight will be measured as appropriate for the participant's age and plotted on age and gender appropriate charts as per SoC at the site, see Section 8.2.1.
- f. Tanner Staging is not needed if early discontinuation from study intervention, only if an early study withdrawal visit.
- g If clinically indicated or required (IRT drug dispensing) at the extra UNS Visit (at any time during the study).
- h. If liver monitoring is required after Day 1, INR should also be performed, see Section 7.1.1 and Section 10.5
- Pregnancy tests will be conducted using urine, unless estimated Glomerular Filtration Rate (eGFR) ≤15 mL/min/1.73m² when a serum human chorionic gonadotrophin (hCG) is required.
- A total of 3 samples to be collected at 0.5 to 1.5 hour, >1.5 to 3 hour, and ≥4 (maximum 8) hour time intervals after taking the first dose of daprodustat, which should be taken in the clinic on Day 1, once the participant is confirmed as enrolled in the study having passed screening.
- k. A total of 4 samples to be collected pre-dose, then at 3 time intervals post administration of the daprodustat dose (which should be taken in the clinic on that day) as follows: 0.5 to 1.5 hour, >1.5 to 3 hour, and ≥4 hour time (maximum 8 hour) intervals. It is recommended that the PK samples are taken at Week 2, but flexibility in collecting these 4 PK samples

TMF-15144431 CONFIDENTIAL

214066

Protocol Amendment 02

is allowed over the first 2 to 4 weeks provided each sample is collected at a different specified time interval]). If a participant has PK sampling deferred to Week 4, but is put on a dose hold at Week 2 (as the Hgb>12.5 g/dL), then the PK sampling should be delayed until the visit after daprodustat is restarted.

1. **For Argentina ONLY**: Pregnancy testing will be performed every 4 weeks for FOCBP as required by local law...

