## 4.6. Hemoglobin Target Range and Frequency of Checks

In adults, the dose of daprodustat is adjusted if required, one step at a time in the range of 1 to 24 mg, to ensure the patient's Hgb is within a target range.

In this study, the target range for Hgb is 10 to 12 g/dL, the same for all ages and regardless of dialysis status (ND or D) or within the D sub-trial population, their dialysis modality (PD or HD).

For pediatric patients, nephrologists dose adjust ESA therapy in accordance with both Hgb and clinical response. At Study Weeks 2, 4, 8, 12, 16, 20, 24, 28, 36, 44 and 52, the Hgb will be checked.

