#### CONFIDENTIAL

214066 Protocol Amendment 02

- In the 3 younger age groups (<12 years), the number of TfOS they may receive in the trial to ensure dosing is well below excipient limits. The weight used for excipient limit calculation in each age group is based on WHO median weights in girls (lighter than boys) minus 2 SD for the youngest child in each age group (i.e., 6 years, 2 years and 3 months).
- The minimum weight used in the PBPK model assumptions, see Section 4.3.
- Relevant for the youngest patients (3 months), the minimum weight also takes
  into account the amount of blood required for study time points relative to
  percentage of blood volume in order to comply with guidance for clinical
  trials in children [Paediatric Population: Recommendations, 2008], see
  Section 8.4.1.

Participants must weigh or exceed the minimum weight required for study entry tabulated for their age group, as indicated in the second column of Table 12:

Table 12 Minimum Weight Per Age Group

Age Group	Minimum Weight Required for Study Entry (kg)	Minimum Weight for TfOS Excipient Limit (based on WHO Weight for Girls, median-2SD) (kg)	Lowest Weight Used in the PBPK Model (kg)
12 to <18 years	25.3	Not applicable b	25.3
6 to <12 years	15.3	15.3	14.6
2 to <6 years	9.8	9.0	9.8
3 months to <2 years	5.0ª	4.5	4.2

Abbreviation: SD = standard deviation

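### Section 8.4.1's assurance of at most 1% of blood volume per day at 5 kg is not supported: on its stated inputs, the four Week 2 PK samples alone use the whole 1%

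*Protocol*

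**What the plan says.** Protocol Section 8.4.1 gives the sample size: "Approximately 1.0 mL of blood (0.5 mL of plasma) is required for the assay". It then bounds PK blood, both for a single occasion and for the whole sampling period, stating that it "will not exceed ~7 mL, ~1.09% of blood volume of a 1 year old child (assuming 80 mL/kg and 8 kg body weight". The next sentence adds the other draws of the first four weeks, invokes the 5 kg entry minimum and concludes that "the total volume of blood required will not exceed the recommended 1% blood volume draw limit per day", or 3% over four weeks.

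The schedule has three post-dose PK samples on Day 1 and four more (one pre-dose, three post-dose) at Week 2 or Week 4. Footnote k of the Schedule of Activities (SoA) states the default: "It is recommended that the PK samples are taken at Week 2". Section 8.4.1 allows an alternative: "The 4 PK samples at Week 2 may also be split between Weeks 2 and 4". If the Week 2 dose was already taken at home, the instruction is "then reschedule the PK sampling to Week 4".

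Safety bloods fall at the same visits. Section 4.6 says: "At Study Weeks 2, 4, 8, 12, 16, 20, 24, 28, 36, 44 and 52, the Hgb will be checked". The SoA lists a full blood count at Week 2. On Day 1 and at Week 4 it lists the count, iron parameters, chemistry and liver tests.

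Section 5.1 says that for the youngest children the minimum weight also takes "into account the amount of blood required for study time points relative to" blood volume. Footnote a to Table 12 raises that minimum from 4.5 to 5.0 kg because of the draw limit.

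**The concern.** The assurance is unconditional and is made for the smallest infants the protocol admits. The only calculation offered beside it is for a different case: an 8 kg child, PK blood only, all seven samples together. Nothing is worked out at 5 kg, for one day, or with the safety bloods included, and neither document gives a volume in mL for any safety test.

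At stake is whether a site that follows the recommended schedule in an infant near 5 kg would keep the promise made in the text. Section 9.4.1 foresaw about four Integrated PK Phase participants aged 3 months to under 2 years in each sub-trial. Section 8.4.2 offers the same sampling schedule to later participants, and Section 10.6.1 makes it compulsory for those in Japan. Only the lightest of these children would be close to the limit.

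**Working it through.** **Inputs.** From Section 8.4.1: about 1.0 mL per PK sample, 80 mL/kg (given for an 8 kg one-year-old), a 5 kg minimum weight, and limits of 1% per day and 3% over four weeks. From the SoA: three PK samples on Day 1, four at Week 2 by default, and a blood count at Week 2. Assumed: 80 mL/kg also at 5 kg, and a count volume v, because the documents give neither.

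**The plan's own figure.** (3 + 4) × 1.0 = 7 mL; 7 / (8 × 80) = 7/640 = 1.09%. It reproduces. As a total over the period it says nothing about one day. As a bound on one occasion it is already above 1%, even at 8 kg. Neither reading supports a 1% daily limit at 5 kg.

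**Week 2 at 5 kg.** Blood volume is 5 × 80 = 400 mL, so 1% is 4.0 mL. Four PK samples take 4 × 1.0 = 4.0 mL = 1.00%, leaving 0 mL. With the count, (4.0 + v)/400 gives:

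- v = 0.25 mL: 1.06%
- v = 0.5 mL: 1.13%
- v = 1 mL: 1.25%
- v = 2 mL: 1.50%

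**Weight at which the day meets 1%.** (4.0 + v) / (0.01 × 80):

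- v = 0: 5.0 kg, exactly the entry minimum
- v = 0.5 mL: 5.63 kg
- v = 1 mL: 6.25 kg
- v = 2 mL: 7.5 kg

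**Sensitivity.** Room left for the count at 5 kg, in mL, is 0.01 × 5 × (mL/kg) − 4 × (sample volume):

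| Sample volume | 80 mL/kg | 85 mL/kg | 90 mL/kg |
|---|---|---|---|
| 0.9 mL | 0.4 | 0.65 | 0.9 |
| 1.0 mL | 0 | 0.25 | 0.5 |
| 1.1 mL | −0.4 | −0.15 | 0.1 |

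**Other days at 5 kg, 80 mL/kg.** On Day 1, 3 × 1.0 = 3.0 mL of PK blood leaves 4.0 − 3.0 = 1.0 mL for that day's panel. If all four later samples move to Week 4, they again take 4.0 mL, and the count, iron, chemistry and liver tests are due at that visit.

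**Splitting the four samples.** Two and two leaves 4.0 − 2.0 = 2.0 mL at each visit. Three at Week 2 and one at Week 4 leaves 1.0 and 3.0 mL.

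**Four weeks at 5 kg.** 3% is 12.0 mL. PK takes 7 mL (7/400 = 1.75%), leaving 5.0 mL for all safety bloods.

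**The case against.** The strongest reply is that the result depends on inputs the documents do not fix. The 80 mL/kg is given for a one-year-old, and using it at 5 kg is an assumption made here. The 1.0 mL is approximate: at 0.9 mL there is a little room even at 80 mL/kg. The count volume is not stated, Section 10.2 leaves the safety tests to local laboratories, and SAP Section 12 refers the PK collection volumes to a manual that is not among the documents. This stands. It rules out the stronger inference that a 5 kg infant on this schedule would certainly exceed 1%. It does not supply the missing demonstration.

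A second reply is that the protocol already has controls: the minimum weight was raised for this purpose, Section 8 promises that blood volumes stay within pediatric recommendations, and the Week 2/Week 4 split lets a site comply. This stands in part. The split is optional and not tied to weight or volume, Week 2 remains the recommended day, and the raised minimum coincides with the weight at which PK blood alone reaches 1%.

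Third, nothing says the count must be drawn on the same calendar day as the PK samples. The Week 2 visit has a window of 3 days either side, and Section 8 permits home assessments. Drawing both at the one visit is nevertheless the natural reading of the SoA.

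A reader might also infer that the printed 1.09% is wrong or that the 3% limit is broken. Neither follows: the 1.09% reproduces, and whether the remaining 5.0 mL is enough over four weeks depends on volumes the documents do not give.

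**Conclusion.** The per-day assurance at 5 kg is not supported by the figures given with it. At 1.0 mL per sample and 80 mL/kg, the recommended Week 2 PK sampling takes exactly 1.00% of blood volume, and the blood count scheduled at that visit has no allowance. The conclusion rests on carrying 80 mL/kg down to 5 kg and taking the approximate 1.0 mL at face value. Modest changes in either restore a fraction of a mL or put PK alone above the limit.

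Severity is minor. SAP Section 8.1 reports that everyone enrolled was aged 12 to under 18 years. At that group's 25.3 kg minimum, four samples are 4.0/(25.3 × 80) = 0.20%. The population PK analysis plan filed with the SAP records four adolescents and a decision not to restart recruitment. No participant and no analysis is affected. The point concerns the correctness of a safety statement and any reuse of the schedule in infants.

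**What to change.** In Section 8.4.1, replace the 8 kg, PK-only example with a short table at 5 kg: totals for Day 1, Week 2 and Week 4, and a four-week total, each including the safety bloods at the volumes laboratories actually need.

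In Section 8.4.1 and SoA footnote k, make the already permitted Week 2/Week 4 split mandatory below the weight at which a day's PK plus safety bloods exceed 1%. Set that weight from the collected laboratory volumes; the 5.63, 6.25 and 7.5 kg above only illustrate counts of 0.5, 1 and 2 mL. The same table should decide how the samples are divided, because Week 4 carries the larger panel and an even split is not shown to fit there.

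Apply the same daily cap in two further places:

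- **Day 1.** Near the minimum weight, rely on Screening bloods taken within the previous 7 days but on a different day.
- **Sampling deferred to Week 4.** Limit the number of PK samples to what fits with that visit's tests.

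The cost is wording in two places, a small table, and collecting the laboratories' minimum volumes. No visits, samples or participants are added. The price is in the PK data: in the lightest infants, trough and post-dose samples may come from different visits or doses, and an occasional sample may be lost in a group planned at about four per sub-trial.
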